## 4. Post-intervention/session 8 and 9:

Static and dynamic balance will be reassessed as previously described to examine retention effects of the VR active gaming intervention (see study calendar). Session 8 will be at least 3-5 days after session 7. Parent/caregiver will return the Nintendo Switch Sports to the researcher. Session 9 will be 4 weeks after session 7. Each session will be for approximately 60 minutes.

# 8.0 Study Calendar

Prior to Day 1	Session 1	Session 2-7	Session 8	Session 9
Familiarization	Familiarization	3-5 days after	Reassessment of	Reassessment of
video	with study tools	baseline	dynamic and	dynamic and
		assessment	static balance 3-	static balance
			5 days after	4 weeks after
			session 7	session 7
			excluding	excluding

			demographic	demographic
			parameters such	parameters such
			as EHI-SF, leg	as EHI-SF, leg
			and arm length,	and arm length,
			weight, height.	weight, height.
Informed	Acquisition of	Intervention	Duration: 1 hour	Duration: 1 hour
consent	demographic	group: Playing		
material,	information	select video games		
Screening		under supervision		
questionnaire		via Zoom		
and ASSQ				
Autism	Baseline	Control group:		
spectrum	dynamic and	Performing		
screening	static balance	standard balance		
questionnaire	assessment	exercises under		
		supervision via		
		Zoom		
Researcher-	Duration: 1.5	Duration: 30- 40		
parent/	hours	minutes per		
caregiver		session		
interaction				

# 9.0 Reportable Events

Any event that requires prompt reporting to the IU IRB per the IU HRPP Policy on Reportable Events will be reported within five business days in compliance the IU HRPP Policy. Minor noncompliance and minor protocol deviations not meeting the requirements for prompt reporting will be reported at time of protocol renewal.

For questions about the rights as a research participant, to discuss problems, complaints, or concerns about a research study, or to obtain information or to offer input, please contact the IU

(Indiana University) Human Research Protection Program office at [contact] or at [contact].

# 10.0 Study Withdrawal/Discontinuation

After reviewing the consent and/or assent form and having their questions answered, participants may decide to sign the forms and participate in the study. Or they may choose not to participate in the study. The decision is up to the participants. If they choose not to participate in this study or change their mind after signing the consent document, it will not affect their usual medical care or treatment or relationship with Indiana University.

If participants change their mind and decide to leave the study in the future, the study team will help them withdraw from the study safely. If they decide to withdraw, they should contact one of the a researchers to make them aware. Researchers will instruct the participant to stop playing the Nintendo Switch Sports and the researcher will collect the gaming console from the participant.

The researchers may stop the participation in the study even if participant do not want to stop if there is any incidence which leads to participant acquiring any exclusion criteria of this study such as any neurological or orthopedic condition affecting balance, epilepsy, or any type of injury that prevents you from continuing your participation during the data collection process of the study.

The PI will be responsible for data and safety monitoring. The study team will meet at least biweekly to discuss any difficulties while conducting the experimental protocols and review the data. [name] will always be available online when data collection is occurring. Minutes of each of the meetings will be maintained on the designated One-Drive folder for the Physical Activity Research lab.

# 11.0 Statistical Considerations

According to prior research study examining the similar paradigm using Xbox games (Ghobadi et al. 2019), we predict the medium effect size (f=0.25) to detect significant changes within groups, between groups and effect of timepoint on static and dynamic balance. Power analysis

(using G\*power 3.1.9.7 software) indicates 14 subjects in each group to have 0.8 power to detect this effect (alpha 0.05). To account for the likelihood of attrition and noncompliance, total 40 participants are being recruited. Data from participants who engage in all the intervention sessions will be included in the analysis.

SPSS (Statistical Package for the Social Sciences) and MATLAB will be used for processing and analyzing the data. Participants demographic and health characteristics will be compared using paired sample t-tests. Intention to treat analysis will be used for addressing effects of treatment or control on static and dynamic balance. The dependent variables for static balance include: 1) sway area of 95% confidence ellipse for center of pressure(mm²), 2) direction of center of pressure sway as anteroposterior and mediolateral (mm). The dependent variables for dynamic balance are: 1) step length (m), 2) stride length (m), 3) step width (m), 4) double support period (sec), 5) cadence (steps/min) and 6) gait velocity (meters/min). Total PBS score will be dependent variable for both static and dynamic balance.

Two-way repeated measures ANOVA (analysis of variance) will be used to determine 1) within intervention and control group, for assessing the main effect of group, 2) between intervention and control group for assessing main effect of time, and 3) between - within interaction for assessing the interaction term. Statistical significance will be declared if  $p \le 0.05$  (two-tailed).

[name] ([contact]) will assist with the statistical considerations.

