Overall, out of the five studies using VR active gaming interventions in youth with ASD, including the previously described studies using some type of control group, three reported it to be beneficial for improving balance and two were inconclusive. Findings from all of these studies are compromised due to 1) lack of randomized controlled trials, 2) lack of objective balance measures, 3) variability in intervention duration, 4) small sample sizes (10-29 subjects), 5) limited game options, 6) lack of clear identification of motor learning/control principles in the research design, (7) variability in game design (i.e. 3 were not commercially available), and 8) no assessment beyond immediate-post intervention. The current published literature does not provide sufficient evidence for the use of VR active gaming as a modality to address postural control/balance deficits in individuals with ASD.

The purpose of this study is to deliver a VR active gaming-based static and dynamic balance intervention to children and youth with ASD that addresses several of the aforementioned gaps in the literature by: 1) using a controlled clinical trial design, 2) using objective measures of static and dynamic balance, 3) using select commercially available VR active games that incorporate specific motor learning principles that impact balance, 4) using a participant sample based on a power calculation to ensure a robust statistical analysis, and 5) assessing retention effects 4 weeks post-intervention. Addressing these gaps will significantly contribute to the knowledge base by verifying if VR active gaming interventions are effective in improving static and dynamic balance in youth with ASD.

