## 2.0 Objectives

# 2.1 Primary Objective

H1: Participation in VR active video gaming incorporating explicit and implicit learning, feedback and knowledge of results, and knowledge of performance motor tenets will lead to increased postural control, as reflected by improved static and dynamic balance. This hypothesis will be tested by Specific Aim 1: to assess the effect of a short-term (3 days/week for 2 weeks) VR active video gaming intervention on static balance, versus traditional balance training exercises, in youth with ASD.

H2: Participation in VR active video gaming incorporating explicit and implicit learning, feedback and knowledge of results, and knowledge of performance motor tenets will reduce the deviation in the spatiotemporal parameters of the gait due to increased dynamic balance and improved motor coordination. This will be tested by Specific Aim 2: to assess the effect of a short-term (3 days/week for 2 weeks) VR active video gaming intervention on spatiotemporal parameters of gait, as a measure of dynamic balance, versus traditional balance training exercises, in youth with ASD.

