# 7.0 Study Procedures

1. Prior to day 1: Informed consent materials, a screening questionnaire, and Autism Spectrum Screening Questionnaire (ASSQ) will be sent electronically to parents/caregivers. Participants and parents/caregivers in both groups will be given access to a video of the data collection space, intervention space setting, and a short introduction of the research personnel for review. If the participants are 18 years or older, this information will be shared with the participants directly and they will fill the questionnaires. If the participant is less than 18 years old, the information will be shared with the parent/legal guardian to be completed. Additionally, The ASSQ is a commonly used valid and reliable 27-item checklist to be filled in by parent/caregiver for assessing symptom characteristics of ASD. The ASSQ can be completed in 10 minutes using a 3-point Likert scale with possible score range being 0 of 54 with 19 being a cut off for a parent/caregiver rating identifying ASD. This tool will be used as a part of demographic screening of the participants prior to the pre-intervention day and used to better describe individual autism symptoms than is available in a medical or educational diagnosis. The researcher will subsequently contact participants and parent/caregiver to review the information, check for understanding, (particularly the terminology used in the ASSQ), assess eligibility via screening tool and address any other questions prior to study inclusion and visit.

Study participation will require 9 visits: 1 pre-intervention visit, 6 intervention visits, 1 post-intervention visits and 1 retention visit. Participants will receive \$10 Amazon or Kroger gift card after completing each session with total possible compensation of \$90.

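### Section 11.0 claims 0.8 power for a between-group effect as well; for the between-group main effect, power is about 0.35 with 28 participants and 0.47 with 40 (three assessments, assumed correlation 0.5)

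*Combined protocol and SAP*

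**What the plan says.** The Combined protocol and SAP, section 11.0 (Statistical Considerations), bases the sample size on a single effect size for three kinds of effect: "we predict the medium effect size (f=0.25) to detect significant changes within groups, between groups and effect of timepoint on static and dynamic balance". The G*Power calculation, it says, "indicates 14 subjects in each group to have 0.8 power to detect this effect (alpha 0.05"). Recruitment is set at 40 to allow for attrition and noncompliance.

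The same section plans a two-way repeated measures ANOVA and lists three tests:

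1. "within intervention and control group, for assessing the main effect of group"
2. "between intervention and control group for assessing main effect of time"
3. "between - within interaction for assessing the interaction term"

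Section 7.0 (Study Procedures) sets the visits as "1 pre-intervention visit, 6 intervention visits, 1 post-intervention visits and 1 retention visit". Balance is assessed at the first visit and at the last two, so there are three measurements per participant.

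Two other places bear on how the power statement will be read. Section 1.0 (Background & Rationale) presents "using a participant sample based on a power calculation to ensure a robust statistical analysis" as one of the gaps in earlier work that the trial fills. Specific Aim 1 in section 2.1 is to assess the effect of a short-term "VR active video gaming intervention on static balance, versus traditional balance training exercises, in youth with ASD", and Specific Aim 2 makes the same comparison for gait.

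**The concern.** One power figure is made to cover three effects that cannot share it. In a repeated measures ANOVA with f and the number of participants held fixed, a higher correlation between a participant's measurements lowers power for the between-group main effect. It raises power for the time effect and for the group-by-time interaction. A sample size that just reaches 0.8 for one kind of effect will generally miss it for the other.

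The between-group main effect is one of the three listed tests, and the power sentence names between-group changes. If power for that test is well below 0.8, a non-significant group effect could be read as the result of an adequately powered test when it is not. The risk is greater because both aims are comparisons with traditional training, and because section 1.0 cites the power calculation as a strength of the trial.

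**Working it through.** **Inputs from the documents.** f = 0.25, alpha 0.05, target power 0.8, 14 per group (N = 28), 40 recruited (section 11.0); k = 2 groups; m = 3 assessments (section 7.0).

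**Assumptions, not in the documents.** Correlation rho between assessments, sphericity factor epsilon, and G*Power's default definition of f. The base case is rho = 0.5 and epsilon = 1, because with m = 3 these values reproduce the plan's 14 per group. The number of measurements actually entered in G*Power is not stated either.

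**Step 1: reproduce the plan's figure (time effect or interaction).** Power comes from the noncentral F distribution with

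lambda = f² × N × m × epsilon / (1 − rho), df = (m − 1) × epsilon and (N − 2) × (m − 1) × epsilon.

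With two groups, the time effect and the interaction have the same degrees of freedom, so they need the same N.

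- N = 28: lambda = 0.0625 × 28 × 3 / 0.5 = 10.5, df (2, 52), power 0.812.
- N = 26: lambda = 0.0625 × 26 × 3 / 0.5 = 9.75, df (2, 48), power 0.778.

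So 28 is the smallest even total that reaches 0.8, which is the plan's 14 per group.

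**Step 2: the between-group main effect under the same inputs.**

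lambda = f² × N × m / (1 + (m − 1) × rho), df = 1 and N − 2.

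- N = 28: lambda = 0.0625 × 28 × 3 / (1 + 2 × 0.5) = 5.25 / 2 = 2.625, df (1, 26), power 0.345.
- N = 40: lambda = 0.0625 × 40 × 3 / 2 = 7.5 / 2 = 3.75, df (1, 38), power 0.471.

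A simulation of this test with 40,000 runs gave 0.346 and 0.472.

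**Step 3: range over the unknown correlation** (m = 3, epsilon = 1).

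| rho | Between-group, N = 28 | Between-group, N = 40 | Time or interaction, N = 28 | Time or interaction, N = 40 |
|---|---|---|---|---|
| 0 | 0.60 | 0.76 | 0.50 | 0.67 |
| 0.3 | 0.41 | 0.56 | 0.66 | 0.83 |
| 0.5 | 0.35 | 0.47 | 0.81 | 0.94 |
| 0.7 | 0.30 | 0.41 | 0.96 | >0.99 |
| 0.9 | 0.26 | 0.36 | >0.99 | >0.99 |

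Every between-group entry is below 0.8. With two measurements instead of three, between-group power over the same correlations runs from 0.44 to 0.26 at N = 28 and from 0.59 to 0.35 at N = 40. Epsilon does not enter the between-group test.

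**Step 4: size of the gap.** For the between-group main effect to have 0.8 power at f = 0.25 with three measurements, the total would have to be 44 at rho = 0, 86 at rho = 0.5 and 120 at rho = 0.9. Equivalently, at rho = 0.5 the test has 0.8 power only for f of about 0.45 with 28 participants or 0.37 with 40.

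**Step 5: could 28 have come from a between-group run?** A search over two or three measurements, correlations from 0 to 0.95 in steps of 0.05, and epsilon of 1, 0.75 and 0.5 gave 28 for the time effect or interaction at several settings, for example (m, rho, epsilon) = (3, 0.5, 1) and (2, 0.6, 1). It never gave 28 for the between-group main effect; the smallest total there was 44.

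**The case against.** The strongest reply is that nothing was miscalculated. The 14 per group is reproduced for the time effect or interaction, and the power sentence refers to a single effect. The ANOVA sentence crosses its labels: it pairs the within-group comparison with the main effect of group, and the between-group comparison with the main effect of time. The author may therefore have meant the interaction by a between-group change. The interaction is also the usual treatment test in a randomised trial with a baseline, since the group main effect averages in the pre-treatment assessment. With the inputs that reproduce 28, the interaction has 0.81 power at N = 28 and 0.94 at N = 40.

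Most of this stands. The sample size is not an arithmetic error, and the interaction reading is possible. But no section names the interaction as the powered effect. The group main effect is listed as a test of its own, and on its plain wording the 0.8 figure extends to between-group changes. The crossed labels explain how the sentence may have arisen; they do not tell the reader which effect was powered.

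Two stronger readings are tempting, and the documents support neither. A reader might infer that the trial is underpowered for its treatment comparison. That does not follow, because the interaction reaches 0.8 under the inputs that reproduce the plan's own number. Its power does depend on unstated inputs: at N = 28 it is 0.66 at correlation 0.3, and 0.72 at epsilon 0.75 with correlation 0.5. A reader might also suspect that one of G*Power's other definitions of f was used, which would give the interaction much less power. With three measurements those definitions need about 80 to 82 participants, so they could not have produced 28.

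**Conclusion.** The point holds for the between-group main effect only. On its plain wording, section 11.0 claims 0.8 power for an effect that does not have it at f = 0.25. Power is about 0.35 with 28 participants and 0.47 with 40, assuming three assessments and correlation 0.5.

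The exact values rest on the assumed correlation, but the conclusion does not. Across correlations from 0 to 0.9, with two or three measurements, and even with all 40 participants analysed, power stays below 0.8.

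This is an over-broad power claim, not a wrong sample size. The calculations do not show that more participants are needed. If the sponsor meant the interaction, the remaining fault is that the sentence does not say so.

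**What to change.** Change the wording of section 11.0 only:

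1. Limit the 0.8 power claim to the effect that the G*Power calculation covered. If that was the group-by-time interaction, name it as the powered treatment comparison.
2. For the between-group main effect, either remove the power claim or give that effect's own lower figure.
3. State the assumptions behind each figure kept: number of measurements, correlation and, for the time effect and interaction, epsilon.

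Suggested text, with blanks for the sponsor to fill from its own calculation:

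> The sample size calculation was run for the [effect] with f = 0.25, alpha 0.05, 2 groups, [number] measurements, correlation [value] and epsilon [value], and gives 14 per group for 0.8 power. It does not cover the between-group main effect [or: the power for which is (value) under the same number of measurements and correlation].

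The sponsor has to retrieve its G*Power inputs, and one listed test will carry a less favourable stated power. Sample size, analysis and conduct do not change.

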In addition to being based on principles of motor learning/control, commercially available VR active gaming can be a cost-effective, at-home intervention. Commercially available systems cost from \$200 to \$1000 for the consoles with an additional \$50 to \$100 for individual games, which could be a one-time investment. About 67% of U.S (United States). households already own at least one VR system^34 and, if there is valid and reliable evidence to support therapeutic outcomes, insurance may pay for these devices. Additionally, children tend to enjoy active gaming and this approach may provide an advantage over traditional therapeutic approaches regarding various accessibility issues (e.g., transportation issues), adherence, and at-home use. Therefore, VR active gaming should be explored further as a stand-alone treatment or an adjunct to conventional balance rehabilitation approaches.

There are few well designed studies using VR-based interventions to address balance in children and youth with ASD. Previous research in this area consists mainly of quasi-experimental studies , which, although useful in providing descriptive information, are limited in providing strong, best-practice evidence. These studies have demonstrated improvements in certain balance variables such as one- and two-footed balance, heel-toe walking distance, and balance components of certain clinical motor assessments (e.g., Movement Assessment Battery for Children-2nd ed, Bruininks-Oseretsky Test of Motor Proficiency, 2nd ed).

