To date only two control group design studies have used VR active gaming-based interventions to improve balance in individuals with ASD. Milajerdi and colleagues compared three conditions in children with ASD (n=20 per group): physical activity intervention, active video gaming, and usual therapies. After 24 sessions over 8 weeks, throwing and catching skills, but not balance skills, improved and there were no differences between conditions. There are several factors that may have contributed to the lack of significant balance skill improvement in this study. First, only one VR game (tennis) was used, and this can be played standing with minimal center of pressure movement, also reducing the variability of training and variability in the task, and consequently restricting motor learning. Second, only providing one game option does not allow for choice and this can impact motivation, participation, and engagement. Third, adherence, enjoyability, and motivation were not reported and therefore no conclusions could be drawn regarding either retention of treatment effects or long-term use.

Caldani and colleagues used an open-case control design to test the hypothesis that short-term balance training using VR would lead to neuroplastic changes in the cerebellum leading to

improvements in postural control in youth with ASD. They compared the effect of 6 minutes of postural control training using 2 customized active-video games with 6 minutes of rest between each trial (n=20 each in intervention and control groups). The specifically designed game consisted of moving a dot on a screen, which represented the participant's center of pressure. The subject moved the dot to either a pre-defined target or to avoid the pre-defined target by standing on a force platform. The control group rested for the duration of the intervention. The researchers reported a reduction in postural sway immediately after the intervention under both eyes open and eyes closed conditions but speculated that the changes were due to test-retest. This outcome could have been predicted and it is unfortunate that the researchers did not plan for this accordingly. This test-retest response limits translation of the intervention over longer duration as the dose, that is duration of the intervention, is insufficient to cause behavioral changes.

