# 3. Intervention/ session 2-7:

Session 2 will occur 3-5 days after the baseline assessment.

3.1: Intervention group: Participants will choose 2 interactive video games on the Nintendo Switch Sports from golf, Frisbee, beach tennis, soccer, Volleyball, badminton, bowling, and chambara. The researcher will supervise the sessions via zoom. These games address motor learning principles as follows. First, they cause movement of the body's center of pressure in mediolateral, anteroposterior-, and diagonal directions without the participant paying active attention to the directional changes, leading to implicit and explicit learning. Second, they display the score achieved by the participant during- and after- each game leading to the participant having knowledge of the performance and the results. Third, playing 2 games provides task and training variability.

Games will be played for 10 minutes each with a 5-minute break in between. The same 2 games will be played each session. Participants will stand at least 3 meters away from the TV while playing the games. Verbal prompts /motivators will be provided during the games. Each session will take approximately 40 minutes. The caregivers will be present at one-hands distance from the participant to prevent any falls. Additionally, participants will be asked to place a chair at a reachable distance which they can hold on to prevent falls. Ideally, each session will occur with an off day in between, however this may not be realistic depending on participant and caregiver schedules and so sessions will occur at participant/caregiver convenience.

Control group: Control group participants will receive balance instruction from the researcher at home via Zoom. The following standard balance exercises will be performed for 15 minutes with 5 minutes of warm and cool down each. Breaks will be given as per the participants' need and verbal prompts/motivators provided. The caregivers will be present at one-hands distance from the

participant to prevent any falls. Additionally, participants will be asked to place a chair at a reachable distance which they can hold on to prevent falls.

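### The f = 0.25 behind the stated 0.8 power is not shown to be a VR-versus-exercise effect, and the 0.8 does not extend to the between-group effect named in the same sentence

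*Combined protocol and SAP*

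**What the plan says.** Section 11.0 opens the sizing with "According to prior research study examining the similar paradigm using Xbox games" (reference 26) and continues "we predict the medium effect size (f=0.25) to detect significant changes within groups, between groups and effect of timepoint on static and dynamic balance". The G*Power result is "14 subjects in each group to have 0.8 power to detect this effect (alpha 0.05". Recruitment is raised to 40 for attrition and noncompliance. The section does not name the F test that was powered, the number of visits entered, the correlation between visits or the sphericity correction. It quotes no mean, SD or contrast from the Xbox study.

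The comparison of interest is set in section 2.1, where Aim 1 concerns the effect of a "VR active video gaming intervention on static balance, versus traditional balance training exercises, in youth with ASD". Aim 2 makes the same comparison for gait. The control arm is active. Section 7.0, under the intervention sessions, says "Control group participants will receive balance instruction from the researcher at home via Zoom" and lists warm-up, balance and cool-down exercises.

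On the evidence base, section 1.0 says "Previous research in this area consists mainly of quasi-experimental studies" and cites the Xbox study there. It then says "To date only two control group design studies have used VR active gaming-based interventions to improve balance in individuals with ASD" and describes references 25 and 37. The Xbox study is neither of these. Reference 25 had a physical-activity arm, an active-gaming arm and a usual-therapy arm of 20 each, and section 1.0 reports that "throwing and catching skills, but not balance skills, improved and there were no differences between conditions".

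**The concern.** Power for a two-arm trial depends on the difference between the arms. Against an untrained or absent comparator, an effect can reflect the whole gain from VR. Against supervised balance exercise, only the excess of VR over exercise counts. The plan uses one value of f for changes within groups, differences between groups and time effects. Those are three different quantities, and one study would not normally give the same f for each. The source study is also one that the protocol's own review leaves out of its controlled evidence.

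The closing part of section 1.0 presents the sample as resting on a power calculation that makes the analysis robust. A reader who accepts 0.8 power for VR versus exercise may give a non-significant result more weight than it deserves. The plan has no confidence-interval or non-equivalence wording to guard against that.

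**Working it through.** **Inputs from the documents.** f = 0.25, alpha 0.05, 14 per group (N = 28) and 40 recruited (sections 6.0 and 11.0). Two equal arms (section 6.0). Three assessments, m = 3: one pre-intervention, one post-intervention and one retention visit (section 7.0).

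**Assumptions.** Correlation between visits r = 0.5 and epsilon = 1. The plan states neither.

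**Step 1: reproduce the plan's figure (group-by-time interaction).** Noncentral F with lambda = f² × N × m / (1 − r), df1 = m − 1 = 2 and df2 = 2(N − 2).
- N = 28: lambda = 0.0625 × 28 × 3 / 0.5 = 10.5, df2 = 52, power 0.81.
- N = 26: lambda = 9.75, df2 = 48, power 0.78. So 28 is the smallest even total that reaches 0.8, which matches 14 per group.
- N = 40: lambda = 15, df2 = 76, power 0.94.

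With two groups, the time main effect has the same lambda and degrees of freedom, so it also gives N = 28 and power 0.81. The stated figure therefore cannot show which of the two was powered.

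**Step 2: the between-group main effect at the same f.** lambda = f² × N × m / (1 + (m − 1)r), df1 = 1 and df2 = N − 2.
- N = 28: lambda = 0.0625 × 28 × 3 / 2 = 2.625, power 0.35.
- N = 40: lambda = 3.75, power 0.47.
- Power of 0.8 would need N = 86.

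For correlation 0.3 to 0.7 the range is 0.42 to 0.30 at N = 28 and 0.56 to 0.41 at N = 40. It stays well below 0.8 throughout.

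**Step 3: what f = 0.25 requires on the interaction.** Let VR out-gain exercise by d SD at both session 8 and session 9. The difference pattern over the three visits is (0, d, d). The pattern (0, 1, 1) has SD 0.471, and each arm carries half the difference, so f = (d / 2) × 0.471. Setting f = 0.25 gives d = 0.25 × 2 / 0.471 = 1.06 SD.

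**Step 4: sensitivity to the interaction effect and the correlation.** These are illustrative effects, because the documents give none for VR versus exercise.

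| Interaction f | Correlation | Power, N = 28 | Power, N = 40 |
|---|---|---|---|
| 0.25 | 0.3 | 0.66 | 0.83 |
| 0.25 | 0.5 | 0.81 | 0.94 |
| 0.20 | 0.5 | 0.61 | 0.78 |
| 0.15 | 0.5 | 0.37 | 0.52 |
| 0.125 | 0.3 | 0.20 | 0.28 |
| 0.125 | 0.5 | 0.27 | 0.38 |
| 0.125 | 0.7 | 0.43 | 0.59 |

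By the formula in step 3, f = 0.125 corresponds to VR out-gaining exercise by 0.53 SD.

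**The case against.** The strongest reply is that the group-by-time interaction is the VR-versus-exercise test in this model, and the plan's 14 per group reproduces for it. If the interaction f really is 0.25, the trial has its 0.8, and more if all 40 complete. That stands. A reader might infer that the stated power has no bearing on the VR-versus-exercise question, but step 1 shows that it does, conditional on the effect.

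A second tempting inference is that f = 0.25 is the VR arm's own change. It would then halve to 0.125 against a control arm that does not change, leaving power of 0.27 to 0.38. The documents do not support this either:
- Quasi-experimental does not mean single-arm. When section 1.0 criticises other studies as uncontrolled, it says so in different words.
- In its list of shortcomings, section 1.0 cites the Xbox study only for lacking objective balance measures. The count of two control-group studies is indirect evidence that it had no comparison group.
- Section 11.0 calls 0.25 a medium effect and gives no data, which also fits a conventional benchmark.
- The halved figure depends on the unstated correlation. At 0.8, f = 0.125 gives 0.60 (N = 28) and 0.77 (N = 40).

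The null result of reference 25 does not settle the matter. Section 1.0 offers reasons for it, including a single tennis game with little center-of-pressure movement and no choice of game. Participants here choose two of eight games. The comparator in that study is described as physical activity, not balance training. It gives no support for f = 0.25, but it does not establish a smaller value.

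Finally, no passage plans to read non-significance as equivalence, so that harm is a risk and not a stated intention. It may also be said that the between-group wording in section 11.0 loosely means the interaction. However, the same section lists a main effect of group among the effects to be tested, so the sentence needs correcting on either reading.

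**Conclusion.** The concern holds as a gap in justification. The protocol gives no basis for f = 0.25 as a VR-minus-exercise effect: its source is outside the review's own controlled evidence, its contrast is not stated, and the comparator here is active. The 0.8 is conditional on a true interaction f of 0.25, about 1.06 SD in favour of VR if the gain is held at both follow-up visits. That figure follows from the definition of f and does not depend on the correlation. The power figures of 0.81 (N = 28) and 0.94 (N = 40) do depend on the assumed correlation of 0.5 and epsilon of 1.

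The 0.8 does not hold for the between-group main effect, where power is 0.35 and 0.47 under the same assumptions. Beyond that, power against exercise is unknown. The documents do not show that the trial is underpowered for its main question, only that the stated power for that question rests on an unsupported assumption.

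**What to change.** Keep 40 participants and revise the wording.

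In section 11.0:
- Name the group-by-time interaction as the powered effect, and state the number of visits and the correlation entered in G*Power.
- Say that f = 0.25 is an assumption about VR against active exercise, not a prediction from the Xbox study. Add that, for a gain held at sessions 8 and 9, it means VR out-gains exercise by about 1.06 SD. If the Xbox study does supply a between-arm contrast, give that contrast and its comparator.
- Drop the claim of 0.8 power for between-group effects.
- Give power for smaller interaction effects as a labelled sensitivity range with its correlation. For example, f = 0.125 gives 0.20 to 0.43 at N = 28 and 0.28 to 0.59 at N = 40 for correlation 0.3 to 0.7.
- Report the VR-minus-exercise difference in change with a 95% CI, and state that a non-significant result will not be read as equivalence.

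In section 1.0, align the statement that the power calculation ensures a robust analysis with the revised text.

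The cost is a few sentences in two sections, with no added participants, visits or procedures. The downside is that the stated power becomes less favourable.
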